6.10.9 Intervention Period Activities

Intervention period activities will be identical to phase-in period activities. As mentioned in **Table 11**, compliance feedback will be shared monthly during coaching calls based upon nursing queries embedded in usual e-documentation (see UH2 Aim 3 and **Table 11** above) that will require a response each shift about whether a bath or shower had occurred and, if so, with what product. For the Decolonization Arm, a negative response will require a reason from a drop down menu. E-reports will be used for chlorhexidine since it is not a prescription drug. Pharmacy records will be used to track dispensing of mupirocin.

In addition to on-site bathing training provided to all intervention hospitals in the phase-in period, we will perform site visits to participating hospitals in either arm based upon requests for assistance, concerns about intervention protocols, or evidence of low compliance. For the usual care arm, evidence of decolonization would constitute “low compliance.” Site visits would be comparable to those used by HCA when implementing other Quality Improvement protocols. In addition, HCA leadership (specifically, the quality performance and infection prevention team that are co-investigators on this proposal) performs routine site visits to all hospitals on a rotating basis and will incorporate encouragement, inquiries, and process assessments related to trial activities and microbiology laboratory submission of isolates (see UH3 Aim 2) during visits to trial hospitals.

Special coaching calls and podcasts on trial rationale will be provided to both arms. As in our previous trial, wound care nurses from HCA hospitals will provide expertise to the Decolonization Arm hospitals during coaching calls and will be reachable for questions throughout the phase in and intervention period.

Investigators will continue to have weekly calls during the intervention phase, as well as active participation in the NIH HCS Research Collaboratory Steering Committee and Collaboratory Work Groups. All activities will be conducted in concert with the HCS Research Collaboratory Coordinating Center (CCC).

6.10.10 Data Acquisition

The Data and Analytics Team will include lead investigators, HCA co-investigators, trial programmer analysts, statisticians, and HCA information technologists. Data pulls will be based upon detailed specifications and will be accompanied by data dictionaries. Data will be pulled from census, microbiology, pharmacy, supply chain, nursing query reports, and administrative data from HCA corporate data warehouses as described in UH2 Aim 4 (Section 5.40). Numerators for most outcome data will be derived from microbiology final result files limited to sterile site specimens from participating hospitals. Denominators will be derived from unit-specific census data. We will also provide descriptive data including demographic and comorbidity data from administrative claims data, compliance data from nursing queries, and product use from pharmacy and supply chain data, and data on use of hand hygiene products, glove, and gown use across arms.

6.10.11 Statistical Analysis

All outcomes will be assessed similarly. Here, we use the example of the primary outcome: clinical cultures with MRSA or VRE (first per patient). MRSA and VRE clinical cultures will be attributed to participating units if the collection date occurred >2 days after admission to that unit through two days after discharge from that unit. This attribution is consistent with CDC guidance for surveillance of nosocomial infections.²⁰⁸

Main trial results will be based upon as-randomized, unadjusted analyses using proportional hazards models to account for patients' variable tenure in the unit. This is necessary for the usual reasons: dichotomizing patients into those with vs. without infections would require us to define a fixed time-frame (within first x days of eligibility, ignoring some infections and omitting patients with shorter stays) or to ignore exposed time (counting infection during unit stay regardless of different length of stay). In addition, power is greater for proportional hazards models than for logistic regression models.^{209 210 211 212}

As discussed with the Statistical Core Working Group of the Collaboratory, clustering within hospital will be accounted for using shared frailties. The frailties are added model terms that allow unique hazards ratios for each hospital, and are necessary to account for clustered randomization.²¹³ Model terms will include individual-level data on arm, hospital, outcome events, trial period (baseline vs. intervention) and an interaction term between trial period and arm. The assessment of trial success will be determined by the significance of the interaction term, which assesses whether the difference in hazard between the baseline and intervention period differs significantly between the two arms. We can write a simple version of the model symbolically as:

$$\lambda_{ij}(t) = \lambda_0(t)e^{\beta_1 Arm_{ij} + \beta_2 Period_{ij} + \beta_3 Arm_{ij} * Period_{ij} + \gamma_i}$$

where i is a hospital, j is a person within the hospital, Arm and $Period$ are indicator variables and are = 0 for patients in a hospital in the control arm or baseline period and 1 if in the intervention arm or period. The overall hazard rate over time for person ij is defined as $\lambda_{ij}(t)$, a function of the baseline hazard $\lambda_0(t)$, which is similar to the intercept in a linear model, times the proportionality for that subject, which is defined by the covariates Arm_{ij} and $Period_{ij}$ and the associated parameters, as well as the frailty, γ_i . The frailties are closely analogous to the random effect in generalized linear mixed models, and account for the clustering (similarity of hazard) within a given hospital. The ultimate effect of the intervention is assessed through β_3 : as parameterized, if it is negative and has p-value < .05 (or 95% CI excluding 0) then the intervention reduces the risk of infection. We plan to assess the need for different frailties by hospital by period (instead of just by hospital), as well as additional clustering by unit within hospital. In addition, we will investigate the need to adjust for the stratified randomization scheme described above in **Section 6.10.53**

Subsequent analyses will include as-treated and covariate-adjusted models. Adjusted models will account for individual characteristics such as age, gender, comorbidities based upon ICD-9 codes, and receipt of intervention products. We will also account for unit type (step down, medical, surgical, etc.) and baseline bathing frequency if this is not balanced after randomization. All analyses will be performed using current versions of SAS (9.4, as of writing, SAS Institute, Cary NC) and/or R (3.0.2, as of writing).²¹⁴

In addressing considerations of interim analyses to determine whether early stopping might be possible, the decision has been made not to pursue an interim analysis for several reasons. First, this trial meets the requirements of a minimal risk study. The study of topical bathing/decolonization therapy necessitates neither interim analyses nor stopping rules since reasonably anticipated adverse events are considered minor. Second, the collection time plus the lag in obtaining data and the relatively sparse power suggest that it is highly unlikely that an early look would result in a stoppage of the trial for either futility or success. Third, the addition of an interim analysis would affect power estimates in such a way to create an elongation of the trial beyond the time period that is acceptable to our health system partner. As described in detail above, participation in the trial requires a continuous assertion that other hospital interventions and campaigns that may conflict with the trial will not be pursued. This restriction to the usual tendency of hospitals to pursue multiple simultaneous interventions for prolonged periods of time was a critical consideration in designing the length and size of this trial. With regard to assessment of adverse events, we have built in a reporting system for both mild and severe side effects, defining study-related events that show no signs of improvement within 7 days of stopping product as serious events. The study-related events monitoring and reporting system is described in detail in our Data Safety Monitoring Plan and in our Decolonization Educational Materials.

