6.10.4 Trial Design and Study Population

[figure not shown]
The ABATE Infection Trial will be a cluster-randomized controlled trial of 54 HCA hospitals, evaluating 2 regimens to reduce HAIs in general hospital adult units (**Figure 1**).

Our intent is to move forward with 54 hospitals to allow for unanticipated withdrawal where a hospital might drop from the trial. For example, early withdrawal from the trial may be required due to a conflicting intervention. Hospitals generally have multiple simultaneous campaigns ongoing to improve patient care. For the ABATE Trial, we require monthly confirmation of either no interventions/ new campaigns at their hospital or a reporting to the Steering Committee of what campaigns or interventions are in consideration or being launched. Should the Steering Committee identify a conflict, the hospital must decide to either withdraw from the trial or not pursue the proposed campaign or intervention. Given that conflicts are likely to arise and hospitals have the option to drop out of the trial despite CEO commitment to the trial, we will proceed with the 54 hospitals with the intent that at least 50 will remain in the trial for the full duration.

The ABATE Infection Trial will employ a 12-month baseline period from March 1, 2013 to February 28, 2014, a 2-month phase in period from April 1 to May 31, 2014 and an 18-month intervention period from June 1, 2014 to November 30, 2015, (NOTE: intervention was extended to a 21-month trial in June 2015, ending February 29, 2016). The unit of randomization will be the hospital, with all participating units within a hospital assigned to the same arm. This preserves the usual structure for quality improvement and avoids confusion of having similar units, often with shared patients and staff, assigned to different protocols.

Since 2007, current practice across all HCA hospitals involves high compliance nasal MRSA screening for the following high risk patients: patients transferred from other facilities (including other acute care hospitals, rehabilitation centers, skilled nursing facilities, assisted living centers), ICU patients, hemodialysis patients, and patients undergoing cardiac, orthopedic, and open spine surgery. Screening compliance has been >90% on serial HCA internal surveys. MRSA+ patients are placed into isolation precautions, which involve assignment to a single room plus gown and glove use by medical staff.

Figure 1: Two study arms of the ABATE Infection Trial

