A summary of the overall study design is found in **Table 8**. Despite the large-scale nature of this cluster-randomized trial, The ABATE Infection Trial will take precautions to adjust for imbalance in confounders or outcomes across the 54 participating hospitals. As described further below, imbalance in the numbers of patients and baseline outcomes will be minimized by a randomization strategy that stratifies by admission volume and baseline multi-drug resistant organisms from a clinical or screening culture (primary outcome) across participating populations in trial hospitals. Residual imbalance in baseline outcomes will be further addressed by including a 1-year baseline period and comparing the changes between intervention and baseline periods between the two arms of the trial (see Analysis Section 6.10.11). As mentioned in UH2 Aim 4, complete data for the baseline period will be obtained from electronic health records and can be obtained after recruitment and after the trial is completed.

Table 8. Key Design Elements of the ABATE Infection Trial

Study Design	Cluster-randomized trial
Unit of Randomization	Hospitals
Study Population	Adults (≥ 12 years old) in one of the following non-critical care units: step-down, medical, surgical, medical/surgical, oncology units
Exclusions	Children (< 12 years old), specialty units, including pediatrics, psychiatry, obstetric/postpartum, rehabilitation/skilled nursing, bone marrow transplant. Units with high utilization of chlorhexidine and mupirocin, including units with $> 30\%$ cardiac/orthopedic surgery patients. Units with mean length-of-stay < 2 days.
Study Period	Baseline Year: March 1, 2013-February 28, 2014 2-Month Phase In Period: April 1, 2014-May 30, 2014 (not included in analysis) 21-Month Intervention: June 1, 2014-February 29, 2016 (NOTE: intervention was extended from an 18-month to 21-month trial, in June 2015)

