6.30.5 Limitations and Planned Solutions

This analysis is limited by the inability to account for all potential confounders that may put one individual at higher risk for hospitalization cost. However, cluster randomization is a major asset for distributing both known and unknown confounders. The availability of data from the baseline period is an additional strength, since each hospital's patient population additionally serves as its own control.

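### The only named alternative to the hospital frailty, read literally, replaces it and would unpair each hospital's two periods; the plan should name the nested form instead

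*Protocol*

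**What the plan says.** Protocol 6.10.11 states that "clustering within hospital will be accounted for using shared frailties". The displayed hazard model, identical in SAP 2.2, has terms for arm, period, their interaction `β3` and one frailty `γ_i` per hospital, common to both periods. Success rests on `β3`: "if it is negative and has p-value < .05 (or 95% CI excluding 0) then the intervention reduces the risk of infection".

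Both documents then name one alternative for this term: "We plan to assess the need for different frailties by hospital by period (instead of just by hospital"). The same sentence describes clustering by unit as *additional*. No equation, correlation structure or decision rule is given for the alternative.

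The design relies on within-hospital comparison. Protocol 6.10.4 says: "Residual imbalance in baseline outcomes will be further addressed by including a 1-year baseline period and comparing the changes between intervention and baseline periods". The arms are then contrasted on that change. Protocol 6.30.5, on the cost aim, says that each hospital's "patient population additionally serves as its own control".

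**The concern.** The sentence uses *instead* for the hospital-by-period frailty and *additional* for the unit term. An analyst who follows those words would drop `γ_i` and fit one independent draw for each of the 108 hospital-periods. That model treats a hospital's baseline and intervention rates as unrelated. Stable differences between hospitals cancel when each hospital is its own control, but here they would enter the variance of `β3`.

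The decisive test is at stake. If the assessment found that a hospital-by-period term was needed and the literal replacement were fitted, a real effect could be declared non-significant. The stated power figures would not describe that analysis.

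**Working it through.** **Inputs from the documents.** Two-sided 0.05 test on `β3`; a "cluster-randomized controlled trial of 54 HCA hospitals"; a 12-month baseline; "intervention was extended to a 21-month trial in June 2015, ending February 29, 2016". Stated power at a 20% effect is 92% for the primary outcome in the initial calculation (18 months). The revised figures are 99.9% for the primary outcome (18 or 21 months) and 85% and 89% for bacteremia (18 and 21 months).

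**Assumptions.** 27 hospitals per arm. The between-hospital SD `τ` and hospital-by-period SD `σ_hp` of the log hazard are not given for these outcomes, and Protocol 6.10.12 says such variances are hard to obtain. Event counts are not given either.

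**1. What the stated power implies.** The figures cannot be rebuilt from raw counts, but their behaviour can be checked. If hospital effects cancel,

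`V_events = (1/E) × (2 + 12/L + 12/(L(1 − e)))`

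where E is events per arm in 12 months, L is intervention months and e is the effect. Power is `Φ(|ln(1 − e)|/√V_events − 1.96)`.

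- Initial primary figure, 92% at L = 18: E = 796, or 29.5 per hospital-year. SE = √(3.5/796) = 0.0663, and 0.2231/0.0663 − 1.96 = 1.405, which returns 92%. The same E predicts 36% at a 10% effect (stated 33%, CI 28 to 37) and 100% at 30% (stated 100%).
- Initial bacteremia figure, matched at 20%: predicts 21% and 97% at 10% and 30% (stated 23% and 98%).
- Revised primary figure, 99.9% at L = 18: SE = 0.0442, or about 66 events per hospital-year.
- Revised bacteremia figure, matched to 85% at 18 months: predicts 87% at 21 months (stated 89%, CI 87 to 90).

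The stated power therefore behaves as if hospital effects cancel and there is no hospital-by-period variation.

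**2. Variance of `β3` under the two forms of the alternative.**

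- Nested (`γ_i + δ_ip`): `V_events + 4σ_hp²/27`
- Literal replacement: `V_events + 4σ_hp²/27 + 4τ²/27`

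**3. Numbers at 60 events per hospital-year, L = 21, e = 20%, `σ_hp` = 0.2.** E = 60 × 27 = 1,620. V_events = (2 + 0.571 + 0.714)/1,620 = 0.00203. Adding 4 × 0.04/27 = 0.00593 gives a nested variance of 0.00795 and SE of 0.0892. Nested power is Φ(0.2231/0.0892 − 1.96) = 71%.

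| `τ` | 4τ²/27 | Replacement SE | Ratio to nested | Power, simulated |
|---|---|---|---|---|
| 0.2 | 0.0059 | 0.118 | 1.3 | 44% |
| 0.3 | 0.0133 | 0.146 | 1.6 | 29% |
| 0.4 | 0.0237 | 0.178 | 2.0 | 13% |

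Simulated nested power is 67% to 71%. As a cross-check, the replacement inflates the reported SE while the true spread of the estimate stays near 0.089. So power is roughly Φ((0.2231 − 1.96 × SE)/0.0892), which gives 47%, 24% and 8%, in line with the simulation.

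**4. Which model would be picked, and its error rate.** In the step 3 setting, a likelihood comparison preferred the replacement to the hospital-only model in 91% to 99% of replicates. Type I error was 35% to 37% for the hospital-only model and 4% to 6% for the nested model. In a separate simulation at `τ` = 0.3 and `σ_hp` = 0.2, it was below 1% for the replacement.

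**5. Wider range.** For the primary outcome, with `τ` from 0.1 to 0.65, `σ_hp` from 0 to 0.3 and 29.5 or 66 events per hospital-year, the SE ratio runs from about 1.04 to 5.9. It is largest when `σ_hp` is zero and shrinks towards 1 as `σ_hp` grows.

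**The case against.** The strongest reply has four parts.

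- **The success test as written is not affected.** This stands. A reader might infer that the planned error bars are already too wide. They are not, because the displayed model keeps `γ_i`, and the alternative is only something whose need will be assessed.
- **Independence is not stated.** This stands in part. The wording also fits two correlated frailties per hospital, which would preserve the pairing, and Protocol 6.10.4 shows that the authors want it preserved. But the two readings give very different answers on the deciding test, and nothing in either document chooses between them.
- **The largest losses belong to settings where the replacement would not be picked.** This stands if the assessment is based on fit, which the plan does not say. With `τ` of 0.2 to 0.4 and a small hospital-by-period SD (0.07 at 60 events per hospital-year for the primary outcome, 0.05 at 25 for bacteremia), the replacement beat the hospital-only model in only 0% to 2% of replicates. A reader might infer a collapse in power to about 5%, as simulated for the primary outcome at `τ` = 0.4 in that setting. The documents give no reason to expect the replacement to be adopted there.
- **Where it would be picked, it errs on the safe side.** This is true for type I error, but a large loss of power remains against a nested model that holds its error rate.

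**Conclusion.** The point holds as a conditional one. The written model is not too wide. The only alternative named for the hospital frailty, taken at its word, discards the pairing that the baseline year was meant to supply and would make the success test too conservative. Where a fit comparison would usually choose it (`σ_hp` = 0.2, `τ` 0.2 to 0.4, 60 events per hospital-year), the SE is about 1.3 to 2 times the nested SE. Power is then about 44% to 13%, against about 70%. All three inputs are assumed, so no single factor can be given as a property of this trial.

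A reader might also infer that the option should be struck out. The evidence points the other way. At `τ` = 0.3 the hospital-only model had type I error of 15% to 17% at `σ_hp` = 0.1 and 30% to 44% at 0.2. Protocol 6.10.12 concedes that its power work generated the same within-hospital correlation in both periods, so that work cannot rule such variation out. The plan offers one model that can be anticonservative and one that, read literally, is too conservative. It does not name the form between them that behaves well.

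**What to change.** In Protocol 6.10.11 and SAP 2.2:

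1. Replace the parenthesis that begins with *instead* by *in addition to the hospital frailty*.
2. Write the alternative out as `λ0(t) exp(β1 Arm + β2 Period + β3 Arm×Period + γ_i + δ_ip)`, with separate variances for `γ_i` and `δ_ip`. Two correlated period frailties per hospital would serve equally well.
3. State that a hospital-by-period frailty without the hospital term will not be used for the success test.
4. Note beside the power tables that 99.9% and 89% apply to the hospital-only model with no hospital-by-period variation.

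The cost is a sentence or two, one model term, and a fitting routine that takes two random effects. No patients or data are needed. When there is no hospital-by-period variation, the SE is slightly wider than with the hospital-only model (0.045 against 0.044 in simulation).
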